
For the walking evaluation subjects are asked to walk at 1.4 m/s for 10 minutes on an instrumented treadmill (Bertec, Columbus, OH) while ground reaction forces are recorded, as well as 3D marker locations and the metabolic data. The marker locations are recorded at a sampling rate of 100 Hz by a 12 infrared camera motion capture system (model: T40s, Vicon Motion Systems Ltd, Oxford, UK). The locations of these markers is chosen to track joint motion.

The treadmill system used for the walking exercise is equipped with parallel bars to prevent any injury to the subject if he were to lose balance and fall. A safety harness attached to the ceiling will also be utilized if the subject makes that request. In addition, a member of the laboratory staff will also accompany the study participant to catch him/her in the event of a fall, if necessary. The participant may ask to rest or to terminate their participation in the study at any time. The socket evaluation session (walking and standing evaluations) should take no more than 4 hours to complete.

The kinematic and force plate data can be combined with inverse dynamics analysis to compute joint angles and moment profiles. Furthermore, analysis between data for the left and right limb and for the conventional and novel socket allows for comparison of symmetry measures. Symmetry indices will be derived for: 1) ankle, knee, and hip joint angle, position, torque time profiles, and 2) the vertical ground reaction forces. The metabolic measurements for standing will be

subtracted from the metabolic rate of walking trials in order to obtain the net metabolic cost of walking.

After the standing and walking exercises subjects will be requested to take off the socket and liner to expose their residual limb skin surface. The consultant dermatologist ([name]) will then inspect the skin and report on skin irritation. The dermatologist will also talk to the subjects on comfort and instruct them to fill out the developed socket evaluation questionnaire. Questions will also relate to points where contact pressure measurements will be made, thus enabling direct comparison of local comfort assessment to pressure findings. Subjects fill out their answers by drawing a line at a desired level for each of the questions. This method allows for post-processing based conversion of the input to numerical data (i.e. 0-100 %) and lacks biases associated with constrained integer number input (e.g. favoring of even/odd numbers).

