Data & Safety Monitoring Plan

All sensor (e.g. force/pressure) data is recorded using data acquisition units (e.g. Arduino Uno, Arduino LLC) connected to dedicated laptop computers. The motion capture data (VICON system) and treadmill data (speed and force plates) are recorded using a dedicated desktop computer. The metabolic cost analysis are recorded on a dedicated data acquisition unit (COSMED) and are subsequently uploaded to a laptop computer.

We will record video (in digital format) for each subject walking for analysis and development purposes. Videos in digital format will be archived in a password protected secure server located at the MIT Media Laboratory. Access to video material will be limited to authorized investigators associated with this study. Video will remain archived in the data server for future reference. Upon subject request, videos can be deleted from server once study is completed.

Benefits

There are no immediate benefits for participating in this study. The prosthetic sockets produced will be prototypes and would not be immediately available.

It is expected that knowledge generated in this study will benefit society. The processes developed for producing 3D printed sockets during this research will be used to understand how to most effectively attach (mechanical) devices to humans. This understanding will aid the development of advanced prostheses, orthoses and other augmentation/rehabilitation technologies.

Risks

Following the inclusion criteria (which include MRI safety) there should be no elevated risk associated with the MRI acquisitions. Other risks and discomforts are minimal as they are those incurred by standing still for 5 minutes, and walking on a treadmill for 10 minutes, both while using either a conventional socket and the 3D printed socket.

There will be a "spotter" standing next to the treadmill and close to the amputee while standing or walking in our facilities. We will give subjects periodic rest/water breaks. Any other necessary assistance to make the subjects comfortable will be provided. If during the standing or walking exercise the subject experiences discomfort such that he/she wishes to terminate the test he/she can decide to do so at any time. To minimize these uncomfortable situations, we will have a certified prosthetist and a dermatologist around during the fitting process during the socket evaluation.

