The dermatologist ([name]) involved in the study will be present during socket evaluation and will judge skin irritation as a function of socket discomfort. Actual harm is unlikely but the researchers,

dermatologist, and prosthetist are present to judge any potential harm. Feedback from the subject can be obtained promptly by researchers present, prosthetist, and/or the dermatologist present. The MIT ethical board (COUHES) will be informed of any adverse circumstances. No follow-up will be made as the procedure poses minimal risk of injury.

Informed Consent

Informed consent will be obtained. The informed consent process will be conducted prior to the initial visit by qualified and approved study personnel. Retention is based upon the decision of each participant to continue with research enrollment. Participants may discontinue at any time without consequence.

VI. DATA ANALYSIS

Personal identifiers

All data and files particular to a subject will be anonymized (subjects will be assigned a code for naming files e.g. subject1_month_day_year) and stored on password protected computers to which only the members of the research group have access.

Data storage

The data will be stored on a password protected computer server in the MIT Biomechatronics Group, Media Laboratory, [name]. Access to this server is secured by a password. Only authorized investigators associated with the study will have access to data.

Treatment of data after study completion

The data will remain in the MIT Media Laboratory secure server for future processing. Upon subject request, digital videos can be deleted from the data server once study is completed.

VII. REFERENCES

- [1] K. Ziegler-Graham, E. J. MacKenzie, P. L. Ephraim, T. G. Trivison, and R. Brookmeyer, "Estimating the Prevalence of Limb Loss in the United States: 2005 to 2050," *Arch. Phys. Med. Rehabil.*, vol. 89, no. 3, pp. 422–429, Mar. 2008.
- [2] J. E. Kurichi, W. B. Vogel, P. L. Kwong, D. Xie, B. E. Bates, and M. G. Stineman, "Factors associated with total inpatient costs and length of stay during surgical hospitalization among veterans who underwent lower extremity amputation.," *Am. J. Phys. Med. Rehabil.*, vol. 92, no. 3, pp. 203–14, Mar. 2013.
- [3] H. E. J. Meulenbelt, P. U. Dijkstra, M. F. Jonkman, and J. H. B. Geertzen, "Skin problems in lower limb amputees: a systematic review.," *Disabil. Rehabil.*, vol. 28, no. 10, pp. 603–608, May 2006.

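### One dermatologist, aware of the socket worn, reports skin irritation, discusses comfort and instructs the comfort questionnaire, so hypothesis components 4 and 5 are not independent evidence

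*Protocol*

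**What the plan says.** Protocol II (Objectives) and V (Methods) list five components of the main hypothesis. Skin irritation, assessed by the dermatologist, is the fourth, and comfort, taken from a questionnaire, is the fifth.

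The dermatologist's part in the evaluation session is spread over two places:

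- **V. Methods, Risks.** To limit discomfort, "we will have a certified prosthetist and a dermatologist around during the fitting process during the socket evaluation". The dermatologist attends the evaluation and "will judge skin irritation as a function of socket discomfort". During testing, "Feedback from the subject can be obtained promptly by researchers present, prosthetist, and/or the dermatologist present".
- **V. Methods, Session 2.** After the standing and walking exercises the dermatologist "will then inspect the skin and report on skin irritation". The following sentence reads: "The dermatologist will also talk to the subjects on comfort and instruct them to fill out the developed socket evaluation questionnaire". The score itself is the subject's: "Subjects fill out their answers by drawing a line at a desired level for each of the questions".

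Both sockets are tested in this one session, in randomized order. The conventional socket is worn with the subject's own liner and suspension, and the novel one with a study liner and sleeve, so anyone present can tell them apart.

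The questionnaire is among the four measurements listed for statistical analysis in Protocol III (Sample Size) and in the SAP. Skin irritation is in neither list.

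**The concern.** Irritation and comfort are the two components that rest on judgement; pressure, gait and metabolic cost are instrumented. If both came out in favour of one socket, a reader would take that as two findings that support each other. That inference needs the two records to be made separately, and the procedure does not ensure it.

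A talk about comfort just before the form is filled in can shift where the subject draws the line. What the dermatologist learns about the first socket can shift the report on the second. The Risks wording, taken literally, goes further and makes the skin judgement depend on discomfort.

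The questionnaire matters most, because it is formally compared between sockets and because Session 2 also plans to set its site-specific answers against the measured pressures. The protocol already takes care over questionnaire bias, since it chose a drawn line to avoid number preference, but it does not control the conversation that accompanies the form.

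**Working it through.** The plan gives no figure on this point. Its calculated requirement of 12 subjects concerns contact pressure and does not enter here. The check is mainly one of sequence.

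**Step 1. Order of events as written.** Call the sockets A (tested first) and B (tested second). Methods has a skin report after each socket test. A paired comparison of the questionnaire also needs one form per socket. Taking Session 2 in the order in which it is written:

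1. Fit and test A (dermatologist on hand, feedback possible)
2. Skin report A
3. Comfort talk A
4. Questionnaire A
5. Fit and test B (as step 1)
6. Skin report B
7. Comfort talk B
8. Questionnaire B

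**Step 2. Which records follow a comfort talk?**

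| Record | Preceded by a comfort talk? |
|---|---|
| Skin report A | No |
| Questionnaire A | Yes (talk A) |
| Skin report B | Yes (talk A) |
| Questionnaire B | Yes (talks A and B) |

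Three of the four records come after a talk with the person who also writes the skin report. Skin report A is exposed only to feedback given during testing.

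**Step 3. Does randomized order remove this?** Only in part. It balances an effect that depends purely on being tested second. It does not balance an effect that depends on which socket the dermatologist or subject knows is being worn, or on what was said about it.

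**Step 4. Order under the fix.** Skin report, then form, for each socket, with the talk held until both sockets are finished: none of the four records follows a comfort talk. If safety requires a talk after A, skin report B and questionnaire B remain exposed, while skin report A and questionnaire A are protected. Feedback during testing is unchanged either way.

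**Step 5. Size, by assumption only.** Take the planned paired t-test, two-sided 0.05, with all 18 subjects complete and no true difference. Let the questionnaire difference be shifted by b SDs of the paired difference. The statistic then follows a noncentral t distribution with 17 degrees of freedom and noncentrality b × √18 = b × 4.243. The rejection probability is the probability of falling beyond ± t(0.975, 17).

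| b | Noncentrality | Chance of a significant result |
|---|---|---|
| 0 | 0 | 5.0% |
| 0.1 | 0.42 | 6.9% |
| 0.2 | 0.85 | 12.6% |
| 0.3 | 1.27 | 22.5% |
| 0.5 | 2.12 | 51.6% |

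Nothing in the documents supports one value of b over another. The shift stands for everything that moves the answers other than the socket's true performance, of which the conversation is only one part.

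**The case against.** The strongest reply is that the procedure is better than a quick reading suggests, and that much of the bias cannot be removed.

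- *Sequence.* A reader might infer that skin is always graded after the subject has reported on comfort. Session 2 lists the inspection first and the talk second, so this does not hold for the first socket. The exposure of the second socket's report stands.
- *The Risks phrase.* A reader might infer that the protocol defines irritation through discomfort. The phrase sits among safety statements, and Methods describes only a written report on skin condition. It may be loose wording for irritation caused by the socket. That is a reason to correct it, not to build a case on it.
- *Presence at fitting.* The text puts the dermatologist nearby in order to limit discomfort. It does not say that the dermatologist observes each fitting.
- *An inflated skin test.* A reader might attach a false-positive rate to the skin comparison. No skin test is planned and no grading scale is given, so there is no such rate. The effect is on a descriptive report.
- *The questionnaire.* The subject scores it and necessarily recognises their own socket. Masking the subject is not realistic, so expectation remains whoever hands out the form. This stands, and it is why the figures in the working cannot be credited to the conversation or to its removal.
- *Masked photographs.* A reader might conclude that a coded re-read is required. With 18 subjects, the same dermatologist could recognise limbs already seen live, so the gain is uncertain.

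Absence of masking is inferred from silence and from the dermatologist's presence; the documents do not use the term open-label. The SAP text ahead of its statistical section was not available for this check.

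**Conclusion.** The concern holds in a limited form. One person who can see which socket is worn writes the skin report, holds the comfort discussion and instructs the questionnaire, and randomized order is the only bias control stated for the comparison. On the order written, three of the four subjective records per subject follow a comfort discussion. Components 4 and 5 therefore should not be read as independent support for each other.

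The size is unknown. The range of 6.9% to 51.6% against a nominal 5% applies only to the questionnaire test, and only for assumed total shifts of 0.1 to 0.5 SD with 18 complete pairs. The documents do not support calling the instrumented outcomes affected, quoting an error rate for skin irritation, or claiming that reordering would remove the subject's own expectations. The conclusion assumes that one skin report and one form are completed per socket, in the order in which Session 2 is written. The change is worth making because it costs almost nothing.

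**What to change.** In Protocol V (Methods, Session 2), state the order after each socket test:

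1. The dermatologist records the skin report first, on skin appearance alone.
2. The subject then completes the questionnaire from a fixed written script, before discussing comfort with anyone.
3. The comfort discussion comes last, after the forms and skin reports for both sockets are complete where safety allows.

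In the Risks section, replace "will judge skin irritation as a function of socket discomfort" with wording under which irritation is judged independently of reported discomfort. State in the protocol that both outcomes are unmasked, and say so when they are interpreted.

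The live skin inspection and safety feedback during testing stay as they are. No staff, visit or equipment is added. The cost is a slightly later research discussion of comfort. Coded photographs read later are optional and not needed for this change.

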# Statistical analysis plan

Statistical analysis of the socket clinical evaluation data will focus on the following measurements:

1. local skin contact pressures
2. metabolic power
3. gait parameters (symmetry indices for joint angles, positions, torques, and ground reaction forces)
4. the socket evaluation questionnaire

For scalar comparisons a paired t-test, with the level of significance set at 0.05, will be used to test for differences between the novel and conventional sockets. For time-series analysis of variance (ANOVA) will be used.

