A total of 18 subjects will be recruited for this study. The worst ratio between the mean and standard deviation for pilot contact pressure measurements for static standing was observed for the mid posterior wall, which presented with a mean of 97 kPa, and standard deviation of 8.9 kPa. If two-tailed t-test based analysis is assumed, aiming to detect at least a 10% difference with respect to this mean, with a significance level of 0.05 and a power of 90%, the theoretically required number of test subjects is 12 (power analysis based on the MATLAB *sampsizepwr* function). However, to increase the chances of significant statistics for all measures (with varying signal to noise ratios), while also anticipating potential candidate drop-out, inclusion of N=18 subjects is proposed here.

Statistical analysis of the socket clinical evaluation data will focus on the following measurements: 1) local skin contact pressures, 2) metabolic power, 3) gait parameters (symmetry indices for joint angles, positions, torques, and also ground reaction forces), and 4) the socket evaluation questionnaire. For scalar comparisons a paired t-test, with the level of significance set at 0.05, will be used to test for differences between the novel and conventional sockets. For time-series analysis of variance (ANOVA) will be used.

Inclusion and exclusion criteria

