In pursuit of our long-term goal, our team has recently developed a framework for prosthetic socket design and fabrication that involves: 1) non-invasive imaging to record patient geometry, 2) indentation to assess tissue mechanical properties, 3) data-driven and automated creation of patient-specific designs, 4) patient-specific finite element analysis and design evaluation, and 5) 3D printing of the end design for clinical evaluation. This study aims to advance these approaches, and clinically assess the overall design process for N=18 transtibial amputees. Socket evaluations are conducted during standing and walking activities. For these evaluations, skin-socket interface pressures are recorded using sensors located at the skin-socket interface. During the walking evaluation, motion capture is used additionally to allow for gait analysis. Furthermore, metabolic cost is measured by indirect calorimetry using an open circuit respirometry system. These experiments are repeated for each patient's conventional socket for comparison. In addition to these quantitative evaluations, each study participant completes a socket evaluation questionnaire, and a certified dermatologist writes a report documenting skin conditions subsequent to each socket test.

The main hypothesis of this proposal is that the novel quantitative socket is equivalent to, or better than, a conventional socket in terms of: 1) skin contact pressures, 2) gait symmetry, 3) walking metabolic cost, 4) skin irritation levels as assessed by the dermatologist, and 5) comfort as evaluated from a questionnaire. Furthermore, we hypothesize that equivalence or improved socket performance can be achieved for all N=18 subjects using a single computational design framework, i.e. that we can formulate the computational design framework such that it can automatically design these sockets for all subjects without requiring algorithm adjustments from one subject to the next.

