During a second session the sockets (designed based on the image and mechanical property data) are evaluated (at the MIT Media Lab's Biomechanics department). In this session both the conventional and novel socket systems will be tested. For all subjects the order of testing (conventional or novel first) is randomized. Subjects are first asked to sit on a chair and expose their residual limb surface for force sensor placement. Recently we established a new inter-socket skin contact pressure assessment system based on flexible pressure and force sensors (A201, 111N, FlexiForce®, TekScan, Boston, MA, USA, and also F-Socket, TekScan, Boston, MA, USA). Data for an array of force sensors can be simultaneously recorded during static standing or dynamic walking exercises. Evaluating loads at select anatomical regions are of interest, these sites include: 1) the medial crest, 2) the fibular head, 3) the tibial crest, and 4) the Mid posterior wall. Sensors are secured to the skin using a thin adhesive tape (12.7 mm wide, 0.0625 mm thick, Scotch Magic®, 3M, USA) which can be removed with minimal discomfort. After sensor placement a liner is rolled over the skin and sensors. The conventional sockets are evaluated with the subject's own liner and suspension system. For evaluation with the novel socket, subjects are fitted with a custom liner (e.g. through Ottobock Healthcare GmbH) or standard commercially available liners (such as the Silosheath Double cushion 3-mm liner, Silipos Holding LLC, Niagara Falls, N.Y, USA). A commercially available sleeve is used for suspension (such as BK Suspension sleeve, Silipos Holding LLC, Niagara Falls, N.Y, USA). Next the compliant socket and rigid outer socket are donned on. For the novel sockets the outer socket is first attached to the subject's conventional foot-ankle system, and alignment is optimized by a certified prosthetists (present during all socket fitting and evaluation procedures) consulted for this study ([name], A Step Ahead Prosthetics). Once subjects have been fitted with the sockets the standing, followed by the walking exercise is conducted. For the walking exercise not only force but also metabolic cost and motion capture data are recorded. The metabolic analysis will provide an assessment of the energy expenditure while wearing either a conventional or the novel socket (discomfort may result in a less efficient or asymmetric gait causing increased energy use). For metabolic cost analysis, subjects are equipped with a breath-by-breath portable telemetric system (Model K4b², COSMED, Rome, Italy). Subjects are also equipped with 46 reflective markers (15 mm diameter) for motion capture (following the Helen Hayes marker model). For the standing evaluation subjects are asked to stand still in an upright position for 5 minutes while skin contact force (or pressure) data and resting state metabolic data is acquired.

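### Low-cost improvement: test order is randomised within one session, but the paired t-test has no order term and no order balance is stated

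*SAP*

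**What the plan says.** The SAP, under Statistical analysis plan, gives one rule for scalar outcomes: "For scalar comparisons a paired t-test, with the level of significance set at 0.05, will be used to test for differences" between the two sockets. The Protocol repeats it in section III, Sample Size. Neither place mentions test order or period.

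The design is in Protocol section V, Session 2 (phase 3). On the evaluation visit, "In this session both the conventional and novel socket systems will be tested", and "For all subjects the order of testing (conventional or novel first) is randomized". No blocking, allocation ratio or equal split is given.

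On timing, "The socket evaluation session (walking and standing evaluations) should take no more than 4 hours to complete", and the Risks section adds "We will give subjects periodic rest/water breaks". No interval between the two socket tests is fixed. The two conditions differ in more than the socket: "The conventional sockets are evaluated with the subject's own liner and suspension system", whereas the novel socket is worn with a custom or commercial liner and a commercial sleeve.

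Only part of the SAP document was available for this review. The remarks below concern the text that could be read.

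**The concern.** This is a two-period crossover completed in one visit. Anything that shifts results from the first test to the second, such as fatigue, treadmill familiarisation, skin state or sensor drift, enters the novel-minus-conventional difference with opposite sign in the two orders. The plain paired t-test then handles it in one of two ways:

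- **Orders balanced:** the shift cancels from the mean difference but stays in its standard deviation. The test becomes conservative and the confidence interval too wide.
- **Orders unbalanced:** part of the shift also moves the estimate.

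The randomisation protects the type I error on average. At stake are precision and protection against a chance imbalance of orders. Order will be known for every subject, so using it needs no new data.

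**Working it through.** **Inputs from the Protocol (III, Sample Size).** The pilot pressure is one "which presented with a mean of 97 kPa, and standard deviation of 8.9 kPa". The target is a 10% difference, two-sided 0.05, 90% power, 12 subjects required and 18 planned.

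**Reproducing the plan's figure.** Target = 0.10 × 97 = 9.7 kPa; 9.7/8.9 = 1.09 SD. Exact non-central t power for a paired test, taking 8.9 kPa as the SD of the paired difference, is 90.2% at N = 11 and 92.9% at N = 12. The stated 12 is therefore adequate on that reading, and N = 18 gives 99.2%.

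**Assumptions not in the documents.** The period effect π is 0.25, 0.5 or 1 SD of the paired difference (2.2, 4.5 or 8.9 kPa). An effect of 0.75 SD stands for a noisier measure. The 1 SD case is a deliberately large value, close to the whole 9.7 kPa target. Nothing in the documents bounds π.

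**Model.** d = τ + sπ + e, with s = +1 or −1 by order and SD(e) = 1. The plain paired t-test (n − 1 df) is compared by simulation with the mean of the two sequence means (n − 2 df).

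**Power with balanced orders**

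| Setting | Plain, π = 0 | Plain, π = 0.25 / 0.5 / 1 SD | Order-adjusted |
|---|---|---|---|
| N = 18, 9:9, τ = 1.09 SD | 99.2% | 98.9 / 98.3 / 93.1% | 99.1% |
| N = 18, 9:9, τ = 0.75 SD | 85.1% | 83.4 / 78.4 / 56.9% | 84.7–84.9% |
| N = 12, 6:6, τ = 1.09 SD | 93.0% | 91.9 / 88.5 / 71.2% | 92.4–92.5% |

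Type I error of the plain test at 9:9 is 4.3 / 2.9 / 0.6%, against 5.0% adjusted.

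**Precision at N = 18, 9:9.** The sample variance of d is inflated by 1 + π² × 18/17:

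- π = 0.25: 1 + 0.0625 × 18/17 = 1.07
- π = 0.5: 1 + 0.25 × 18/17 = 1.26
- π = 1: 1 + 18/17 = 2.06

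The approximate 95% half-width is t × 8.9 × √(inflation/18). This gives 4.57 / 4.98 / 6.35 kPa for the plain test, against 4.45 kPa adjusted and 4.43 kPa plain with no period effect. Dividing 18 by the inflation, the plain test uses the information of 16.9 / 14.2 / 8.7 subjects.

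**If order were assigned by simple randomisation** (not stated; the Protocol's wording also fits blocking). With Binomial(18, 0.5), P(exactly 9:9) = 18.5% and P(12:6 or worse) = 23.8%. At 12:6 the bias is (12 − 6)/18 × π, that is 1.48 kPa at 0.5 SD and 2.97 kPa at 1 SD. The conditional type I error at π = 0.25 / 0.5 / 1 SD is 5.7 / 7.0 / 8.6%. Averaged over the randomisation it stays at 5.0%.

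**The case against.** The strongest reply is that a paired t-test with randomised order is a legitimate analysis, and that at N = 18 and the plan's own target it loses almost nothing: 98.3% against 99.1% at an assumed 0.5 SD. The fall below 90% needs both that period effect and the loss of about a third of the sample. At 0.5 SD, plain-test power is still 93.7% at 7:7 and 96.7% at 8:8. This stands, and it is why the point is an improvement and not an error.

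Second, no period effect is shown. The session leaves room for recovery: up to 4 hours for about 15 minutes of standing and walking per socket, changes of liner and socket, rest breaks, and a skin check after each ("a certified dermatologist writes a report documenting skin conditions subsequent to each socket test"). Net metabolic cost subtracts standing from walking, and symmetry indices compare limbs, so some common drift may cancel in those outcomes. This also stands. A period effect is neither shown nor excluded, and the kPa figures apply to pressure only.

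Third, the order term can cost power. With simple randomisation and no period effect, power for 0.75 SD is 82.4% adjusted against 85.0% plain; at a 12:6 split it is about 80% against 85%. That is a reason to pair the term with a balanced list, not a reason to ignore order.

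Fourth, the term does not remove unequal carry-over, which is possible because liner and suspension differ between conditions. An assumed carry-over difference of 0.5 SD biases both estimates by 0.25 SD (0.25 × 8.9 = 2.2 kPa). Type I error is then 17.0% adjusted against 15.6% plain. With an added 0.5 SD period effect it is 16.9% against 7.4%, because the plain test's inflated error term hides part of the bias.

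Finally, all the power figures are for a test of difference, whereas the main hypothesis is that the novel socket is at least as good. The confidence-interval widths carry over to that question; the power figures do not do so directly.

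**Conclusion.** The point holds as a recommended, inexpensive improvement. The planned test is valid, but it ignores a factor that the design randomises. The gain is below one power point at N = 18 and the plan's target for period effects up to 0.5 SD. At 0.5 SD it is about 6 points for the noisier measure and about 4 points at 12 subjects. These are the two situations the Sample Size section itself anticipates in raising N from 12 to 18: measures that vary in signal-to-noise, and drop-out.

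The sizes rest on an assumed period effect, on 8.9 kPa being the SD of the paired difference, and on there being no order term or balanced list in the part of the SAP that was not available. Confidence is medium for these reasons.

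**What to change.** Make two changes together, before any order is assigned.

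1. **Balanced list.** Assign order from a list with 9 subjects starting on each socket, for example in permuted blocks so that balance roughly holds if recruitment stops early.
2. **Order-adjusted analysis.** For each scalar outcome, regress the within-subject difference (novel minus conventional) on test order coded +1/−1. Report the intercept, which is the mean of the two sequence means, with its 95% confidence interval as the socket effect. A mixed model with socket, period and random subject would also serve. Fix this in advance and do not make it depend on a preliminary test for a period effect.

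**Cost.** An order list and a few lines of SAP text, with no new data. One degree of freedom is spent (17 to 16 at N = 18). With no period effect this is about 0.3 power points at 9:9 (0.75 SD) and 0.5 points at 6:6 (1.09 SD). If drop-out leaves 9:6, the variance rises by 15²/(4 × 9 × 6) = 1.042, or 4.2%, and power for 0.75 SD is 75% adjusted against 77% plain. With 9:9 the term pays once the period effect is just above 0.1 SD; without a balanced list, only above roughly 0.25 to 0.3 SD. The SAP should also say that the adjustment does not address unequal carry-over.
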